#### Date: 17 October 2022

#### 4.4 Termination of the entire trial

Premature termination of the clinical trial will be considered when the risk-benefit ratio changes markedly for the patient, the use of the study medication is no longer justifiable, the sponsor believes it is necessary to terminate the clinical trial for safety reasons, when early evidence of the superiority or inferiority of a treatment group is obtained by an interim analysis or by other research results, or when the clinical trial proves to be impracticable.

#### 4.5 Unblinding

In the case of a requirement to unblind study medication, one of the chief investigators needs to be informed to discuss the unblinding. The unblinding list is held by the Institute of Medical Informatics, Statistics and Documentation (IMI), Medical University of Graz, which is not involved in study investigations.

## 4.6. Tracking of drop out patients

In order to guarantee a 100% follow-up of the mortality in this study, we would like to apply to be able to call up the mortality data of the study participants from Statistics Austria for the period of study participation. This can increase the quality of the data even further and thus improves the significance of the study.

## 4.7. Query of mortality data

In the beginning of the year 2023, the study team would like to request a query from Statistic Austria regarding the mortality of the participating study patients.

## 5. VISIT PROCEDURES, MEASUREMENTS AND ASSESSMENTS

#### 5.1 Recruitment and screening

Sites will recruit competitively and sites will receive compensation for their work based on a per-patient fee. The clinic staff of the intensive care unit informs patients about the possibility of being enrolled in this study. No study-related procedures are undertaken before obtaining informed consent. The study team in detail explains the study procedures and asks the participant about their willingness to participate in this research study. After informed consent is signed and obtained, participants are given a signed copy of the informed consent document and are assigned a screening identification number.

After obtaining informed consent at the screening visit, subject's eligibility will be further assessed and documented by using a source data form with a list of inclusion and exclusion criteria, medical history (including all medications past and current) will be acquired and the following measurements will be performed: body weight, height, blood pressure, ECG and blood parameters (see Table 2). Laboratory results up to 2 days before screening can be used to test eligibility for the trial.

Subjects unable to provide written informed consent will not be included in the study.

Protocol No: Version 2.17

#### Date: 17 October 2022

#### 5.2 Randomisation

After screening, all eligible patients for the trial will be randomised into one of the two arms of the study via Randomiser Software (Institute for Medical Informatics, Statistics and Documentation, Medical University of Graz, http://www.randomizer.at), which will be programmed with a randomisation schedule provided by an independent statistician. The randomisation will be stratified by site, type 2 diabetes and by sex.

Only the subject number and subject initials will be recorded in the case report form (CRF). The investigator will maintain a personal subject identification list (subject numbers with the corresponding subject names) to enable records to be identified.

A summary of all visits and procedures has been outlined below (Table 1). A more detailed description of each visit and accompanying procedures can be found later in the protocol (5.4 - 5.5)

#### 5.3 Visit schedule

	Visit 1 (V1) Screening / Baseline	Visit 2 (V2) (week 6 ± 2)	Visit 3 (V3) (week 12 ± 2)	Visit 4 (V4) (Week 26 ± 2)	Visit 5 (V5) (4 weeks ±1w after V4)
Informed Consent	X				
Inclusion/exclusion criteria	X				
Randomisation	Х				
Demography, medical history	х				
Concomitant medication	Х	Х	Х	Х	
Vital signs	Х	х	Х	Х	
Height	Х				
Weight	Х	х	х	Х	
Physical examination	х	х		Х	
ECG	х				
Cardiac ultrasound	Х	Х		Х	
Biobank sampling	Х	Х		Х	
nt-proBNP (local)	Х	х	х	Х	
Blood sampling	Х	х	Х	Х	
Liver function parameters (AST, ALT, GGT)	Х	х	Х	Х	
Renal function parameters (creatinine, eGFR)	Х	х	Х	Х	
Adverse Events		Х	Х	Х	Х

#### Protocol No: Version 2.17

#### Date: 17 October 2022

Dispense medication	Х			
Drug accountability			Х	
Safety assessment before discharge	Х			

Table 1 Visit schedule

## 5.4 Visit procedures

#### Visit 1 - Screening/Enrolment Visit (Day 0 - hospital stay)

- Obtain informed consent of potential participant verified by signature on study informed consent form (10.5)
- Collect blood to check inclusion criteria (creatinkinase, troponin T (or troponin I), eGFR, blood pH, nt-proBNP) (5.5.7)
- Collect and prepare blood samples for biobank (5.5.6)
- Perform echocardiography (5.5.7)
- Obtain demographic information, medical history, medication history, alcohol and tobacco use history (5.5.1)
- Record vital signs (5.5.3)
- Measure body weight and body height (5.5.4)
- Verify inclusion/exclusion criteria (4.2 and 4.3)
- Randomize the subject (5.2)
- Dispense the study medication for trial period (9.4)
- Adjust concomitant antihyperglycemic medication
- Assessment of side effects and patient safety before discharge (5.5.8)

## Visit 2 - Follow up 1 Visit (Week 6 ± 2 weeks)

- Record adverse events as reported by participant or observed by investigator (6.1 6.6)
- Record vital signs (5.5.3)
- Measure body weight (5.5.4)
- Collect blood for routine biochemistry (5.5.5)
- Perform echocardiography (5.5.7)
- Record changes in medication
- Collect and prepare blood samples for biobank (5.5.8)

#### Protocol No: Version 2.17

#### Date: 17 October 2022

- Record adverse events as reported by participant or observed by investigator (6.1 6.6)
- Record vital signs (5.5.3)
- Measure body weight (5.5.4)
- Collect blood for routine biochemistry (5.5.5)
- Record changes in medication
- Record participant's adherence to treatment program

#### Visit 4 - Follow-up 2 Visit (Week 26 ± 2 weeks)

- Record adverse events as reported by participant or observed by investigator (6.1 6.6)
- Record vital signs (5.5.3)
- Measure body weight (5.5.4)
- Collect blood for routine biochemistry (5.5.5)
- Perform echocardiography (5.5.7)
- Record changes in medication
- Collect and prepare blood samples for biobank (5.5.6)
- Record participant's adherence to treatment program
- Drug accountability (5.5.11)

## Visit 5 - Telephone assessment (4weeks ± 1week after V4)

■ Record adverse events as reported by participant (6.1 – 6.6)

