#### 4.3 Withdrawal criteria

Subjects may be withdrawn from the study at the discretion of the Investigator or Sponsor due to a safety concern or if judged non-compliant with trial procedures. A subject must be withdrawn from treatment of the following applies:

- Subject chooses to withdraw from the study at any time
- Adverse event requires unblinding of the study medication
- Pregnancy or intention of becoming pregnant
- Intolerable adverse effects
- Major violation of the study protocol
- Occurrence of an exclusion criterion
- Other circumstances that would endanger the health of the subject if he/she were to continue his/her participation in the trial.

Reasons for withdrawals and discontinuation of any subject from the protocol have to be recorded.

Protocol No: Version 2.17

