#### 6.1 Adverse Event description

For the purposes of the study, AEs will be followed up according to local practice until the event has stabilised or resolved, or the Follow-up Visit, whichever is the sooner. SAEs will be recorded throughout the study.

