#### 6.6.1 Reporting of SAEs

The Sponsor shall report (i.e., from signing the informed consent onwards through the trial defined follow-up period <please define>) all SAEs and non-serious AEs which are relevant for a reported SAE and Adverse Events of Special Interest (AESI) by fax or other secure method using BI IIS SAE form to the BI Unique Entry Point immediately (within twenty four (24) hours or next business day whichever is shorter).

BI Unique Entry Point:
Boehringer Ingelheim RCV GmbH & Co KG,
Pharmacovigilance Austria
[name], [name], Austria

[contact] [contact]

E-mail: PV local [contact]

For each adverse event, the investigator will provide the onset date, end date, intensity, treatment required, outcome, seriousness, and action taken with the investigational drug. The investigator will determine the expectedness of the investigational drug to the AEs as defined in the Listed Adverse Events section of the Boehringer Ingelheim's (BI's) Investigator Brochure for the Productor BI Drug Information e.g. Summary of Product Characteristics (SmPC) or Product Information (PI) for the authorised Study Drug provided by BI,

The investigator does not need to actively monitor patients for adverse events once the clinical trial has ended. However, if the investigator becomes aware of an SAE(s) that occurred after the patient has completed the clinical trial (including any protocol specified follow-up period), it should be reported to BI if investigator considers it as relevant to the BI study drug.

Protocol No: Version 2.17 Date: 17 October 2022

The sponsor will report the SAE to the ethics committee and the local authorities as well as Boehringer Ingelheim Pharmacovigilance in accordance with the aforementioned SAE reporting instructions.

A suspected unexpected serious adverse reaction (SUSAR) is designated as such according to Guideline 2001/20/EG. A serious adverse reaction is deemed unexpected when it is not listed in the corresponding basic document (Summary of Product Characteristics, IB, IMPD).

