#### Date: 17 October 2022

#### 9. TREATMENT

#### 9.1 Study medication

Empagliflozin is a sodium-glucose cotransporter 2 (SGLT2)-inhibitor. It works by increasing the amount of sugar that leaves the body in the urine. The study dose is 10mg once daily in the morning, taken with or without food. Each tablet contains 10mg Empagliflozin or Placebo. The pharmaceutical form is a round, pale yellow, biconvex, beveledged film-coated tablet debossed with "S10" on one side and the Boehringer Ingelheim logo on the other (tablet diameter: 9.1 mm). Empagliflozin has minor influence on the ability to drive and use machines. Patients should be advised to take precautions to avoid hypoglycemia while driving and using machines, in particular when Empagliflozin is used in combination with a sulfonylurea and/or insulin. Pharmacy (Anstaltsapotheke) at the University Hospital of Graz, Austria will pack the medication as 26 weeks supplies for study participants and label study medication according to current regulatory requirements.

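### Visit 5, the only scheduled safety contact after treatment, is dated solely from Visit 4, so a patient who leaves the study before Visit 4 has no dated post-treatment contact

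*Protocol*

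**What the plan says.** Protocol 5.4 lists the last contact as "Visit 5 - Telephone assessment (4weeks ± 1week after V4"). It is a telephone call with one task, recording adverse events. The schedules in Protocol 5.3 and SAP 3.4 give the same timing. The visit it is dated from is "Visit 4 - Follow-up 2 Visit (Week 26 ± 2 weeks"). Protocol 9.1 says the pharmacy "will pack the medication as 26 weeks supplies for study participants", so for a completer Visit 4 falls at about the end of treatment.

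On early stopping, Protocol 4.3 says "A subject must be withdrawn from treatment of the following applies", and its list of reasons includes "Intolerable adverse effects". The only record it asks for is this: "Reasons for withdrawals and discontinuation of any subject from the protocol have to be recorded". No early-termination visit, and no contact dated from the last dose, appears in either document. Sections 4.6 and 4.7 deal with drop-outs through a query of national mortality data.

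On how long events are pursued, section 6.1 says "AEs will be followed up according to local practice until the event has stabilised or resolved, or the Follow-up Visit, whichever is the sooner". Section 6.6.1 gives the period for reporting to the manufacturer as running "from signing the informed consent onwards through the trial defined follow-up period <please define>", so its end was never filled in.

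**The concern.** An end-of-treatment safety call exists to pick up events that appear, or come to light, after the drug is stopped. Here it is tied to a visit that early leavers do not attend. A completer gets a call about 4 weeks after the last dose. A patient who stops because of an adverse effect and leaves the study gets no scheduled call.

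Serious events, ketoacidotic events and genital infections are named safety objectives in both documents. The SAP's safety section tabulates deaths and serious events, with ketoacidosis included, as number and frequency per arm, and states no adjustment for length of follow-up. Its section on extent of exposure (8.1) is itself unfilled template text. Unequal ascertainment would pass straight into those tables. If early departures differed between arms, so could the chance of an event being recorded.

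**Working it through.** **1. The plan's own dropout figure.** This is the only number in the documents that bears on how many patients may leave early.
- Inputs: Appendix A gives means of 653.66 and 282.66 (difference 371.0) and SDs of 772.98 and 289.60. Section 7.1 gives a 40% relative difference and a correlation of 0.85.
- Δ = 0.4 × 371.0 = 148.4.
- Variance of the change = 772.98² + 289.60² − 2 × 0.85 × 772.98 × 289.60 ≈ 300,813, so the SD is 548.5.
- n per arm = 2 × (1.960 + 0.842)² × 300,813 / 148.4² ≈ 2 × 7.85 × 13.66 ≈ 214.5, rounded up to 215. The plan states 216, so it is reproduced to within one patient.
- 216 × 1.10 = 237.6, rounded up to the stated 238 per arm.
- Allowance: 238 − 216 = 22 per arm, 44 in total, and 44/476 = 9.2%. Taking 10% of 476 directly gives 47.6, so about 44 to 48 patients for all reasons combined.

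**2. When Visit 5 falls.** Visit 4 is at weeks 24 to 28. Visit 5 is 3 to 5 weeks later, so at week 24 + 3 = 27 to week 28 + 5 = 33, nominally week 30.

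**3. Three patients compared.**
- *Completer.* Visit 5 comes about 4 weeks after the end of treatment.
- *Stops the drug at, say, week 3 and stays.* Visits 2 to 5 remain. Visit 5 is nominally 30 − 3 = 27 weeks after stopping (range 24 to 30), which is more off-drug observation than a completer has.
- *Stops at week 3 and leaves.* There is no Visit 4, so Visit 5 has no date.

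**4. What else covers the third patient.**
- An event already known is followed under 6.1. An event of special interest is followed under 6.5, with repeat creatinine testing in 6.5.2 and work-up of acidosis in 6.5.3.
- Death is covered by the planned query in 4.6 and 4.7.
- A later serious event is reported under 6.6.1 only if the investigator happens to learn of it and thinks it relevant to the drug.
- A new non-fatal event after departure is not looked for under any section.

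**5. Whether another section supplies an end date.**
- 6.1 records serious events for the duration of the study but sets no end for the individual patient.
- 10.7 ends the trial at the last subject's Visit 5, which is a trial-level end.
- 6.6.1 has a blank placeholder.
- 6.1 ends follow-up of adverse events at a follow-up visit that it does not number. Visits 2 and 4 both carry that label, and 10.7 describes Visit 5 in similar terms. Even if Visit 5 is meant, it is undated for someone without Visit 4.

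**The case against.** Several stronger readings are tempting, and the documents do not support them.

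- *That patients who stop because of harm get no safety follow-up.* Sections 6.1, 6.5 and 6.6.1 require or allow follow-up of known events and of late serious events that come to light. The event that caused the stop is not abandoned, least of all ketoacidosis, for which 6.5.3 is explicit.
- *That stopping the drug means losing the call.* The analysis is by intention to treat, and SAP 5.2.2 lists low drug exposure and a missing week-26 evaluation as separate per-protocol exclusions. Patients who stop but stay are therefore foreseen. Section 4.3 does blur leaving treatment with leaving the study.
- *That 44 patients would be missed.* That figure is an all-cause allowance for the week-26 analysis. It is not a count of patients leaving because of harm, and it is not a firm ceiling.
- *That the safety comparison is biased.* The documents give no withdrawal rate by arm and no rate for any of these events. One missed event in 238 would be 1/238 = 0.42 percentage points, but that is arithmetic on a hypothetical event.
- *That renal safety data are lost through the missing call.* Visit 5 is a telephone call without laboratory tests, so re-dating it recovers no creatinine or eGFR.

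It is also fair to say that 10.7 offers a natural reading of the follow-up visit in 6.1, that 6.5.3 can be read as a specific rule beside a general one, and that the blank in 6.6.1 governs reporting to the manufacturer rather than all recording of serious events. Those are drafting points and would not carry the finding alone.

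What stands is that no scheduled post-treatment contact exists for patients who leave before Visit 4.

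**Conclusion.** The gap is real but limited. It concerns patients who leave the study entirely before Visit 4, and within that group new non-fatal events after departure. The size is not known from the documents; about 44 of 476 is a rough planning guide, on the assumption that early leavers make up most of the all-cause dropout allowance. A difference between arms is possible if departures differ by arm, but nothing in the documents shows one, and a reader should not infer that the safety tables are biased in either direction. The primary efficacy analysis is not touched. This is an inexpensive improvement in safety ascertainment, not a defect that undermines the trial.

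**What to change.** - In Protocol 5.3 and 5.4 and SAP 3.4, date the existing Visit 5 call from last dose for any patient who leaves before Visit 4, keeping the existing 4 weeks ± 1 week.
- In 4.3, state that withdrawn patients are asked for this call unless they refuse further contact, and separate leaving treatment from leaving the study.
- In consequence, name that contact as the end point in 6.1 and in place of the blank in 6.6.1, and reconcile 6.1 with 6.5.3.

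The cost is a wording amendment and a few extra telephone calls of a kind already scheduled. Recovery will be partial, because some leavers will refuse.

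The calls may no longer be possible. The synopsis gives last patient out as 3 May 2022 and database lock as 17 May 2022, while this version is dated 17 October 2022. Those dates need checking themselves: last patient in is given as 10 December 2021, and 144 days (20.6 weeks) to last patient out is shorter than the 24 weeks to the earliest Visit 4. If follow-up has closed, report by arm how many patients had no post-treatment safety contact, beside the safety tables. The corrections to 6.1 and 6.6.1 remain worth making.

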#### 5.5 Description of procedures and measurements

## 5.5.1 Medical history and physical examination

A medical history will be performed at the screening visit to record illnesses, disorders and medications. This information needs to be updated on all follow-up visits.

Physical examination will be performed at the Screening visit (study visit 1) according to local procedure. During this visit the physician will perform a physical examination with the focus on cardiac, lung and abdominal examination. Any abnormal, clinical significant findings must be recorded in the SDF (Source Data Form) as well as in the eCRF (Clincase). Any changes in subsequent visits as compared to the screening visit which fulfils the criteria of an AE must be recorded as an AE. Any changes in concomitant illness will be recorded as changes in medical history. Any changes in medications will be recorded in the eCRF.

Protocol No: Version 2.17

#### Date: 17 October 2022

## 5.5.2 ECG

An ECG will be performed at the screening visit. The ECG will be interpreted, signed and dated by the investigator before randomisation.

## 5.5.3 Vital signs

Pulse should be recorded at all visits after resting for five minutes in a sitting position. Systolic and diastolic blood pressure will be measured in sitting position at all visits.

## 5.5.4 Body weight and height

Weight should be measured at all visits. The same and calibrated pair of scales should preferably be used throughout the trial. Height will be recorded at the screening visit. BMI (body mass index) will be calculated as follows: BMI = weight (kg)/height (m^2).

## 5.5.5 Routine biochemistry

Blood samples will be obtained at all visits after an 8 hour fast and processed by the local laboratory using standard methods' for routine tests. Patients can take their regular morning medications but are asked that they do not take any of their diabetes medications on the morning of their study visit. Patients should bring their regular medication along to their study visits to be further advised by the doctor. See table 2 below for a detailed description of blood collection at each visit:

Blood test	Visit 1	Visit 2	Visit 3	Visit 4
Hematology (full blood count)	X	X	X	X X
HbA1c	X	X	X	X
	X	X	X	X
Sodium, Potassium, Chloride				
Calcium	X	X	X	X
Phosphate	X	X	X	X
Magnesium	X	X	X	X
Iron, Ferritin, Transferrin	X	X	X	Х
Creatinkinase	X	X	X	X
LDH (Lactatdehydrogenase)	X	X	X	X
AST (Aspartate-Aminotransferase)	×	X	X	x
CK MB	Х	Х	Х	х
ALT (Alanine-Aminotransferase)	Х	Х	Х	Х
GGT (Gamma-Glutamyl-Transferase)	Х	X	Х	X
CRP (C-reactive Protein)	X	X	X	Х
Creatinine	Х	Х	X	X
eGFR	X	X	X	Х
Total cholesterol	Х	X	X	Х
Triglycerides	Х	X	X	Х
HDL (high density lipoprotein)	Х	X	X	Х
LDL (low density lipoprotein)	X	Х	X	Х
Troponin T (Troponin I)	Х			
NT-pro BNP	X	X	x	_X

#### Protocol No: Version 2.17

#### Date: 17 October 2022

Fasting glucose	Х	Х	Х	Х
Myoglobin	X			
pH (arterial/venous)	Х			
Urine Albumin/Creatinine Ratio (ACR)	Х	Х		Х

Table 2 Summary of blood tests at each study visit

## 5.5.6 Blood sample collection and plasma extraction for biobanking

Blood will be collected via venous puncture into 16ml serum, 6ml EDTA and 4ml sodium citrate vacutainers and centrifuged within 30 min of collection. Plasma should be transferred into Eppendorf tubes and stored at -80°C locally. In regular intervals these samples will be shipped on dry ice to the Biobank of the Medical University of Graz, where they will be stored at -80°C for future biomarker analyses. NT-proBNP and blood ketone bodies will be measured in batches from these stored biomarker samples.

#### 5.5.7 Echocardiography

Echocardiography will be performed using locally available ultrasound devices. Left ventricular wall thickness and chamber diameter will be assessed. Left ventricular systolic function will be assessed in 4- and 2-chamber views using the modified Simpson's rule. Regional systolic dysfunction will be classified using the WMSI (wall motion score index) and/or strain measurements. Left ventricular diastolic function will be measured using E as well as lateral and septal e'. Right ventricular function will be evaluated using Tricuspid Annular Plane Systolic Excursion (TAPSE). Left atrial volume index will be calculated from LA dimensions. Colour flow Doppler as well as continuous as well as pulsed wave Doppler will be used for detection of valve diseases. A detailed overview on the EMMY trial echocardiography sub-study is given in the Echo Manual (please see Appendix C).

## 5.5.8 Assessment of side effects and patient safety before discharge

Physical examination and a check of possible side effects will be performed before discharge at study visit 1.

